5.0 Study Design and Procedures

5.1 Schedule of Events:

| Procedures | Screening Period | Visit #1 | Telephone Call | 8-10 weeks after Visit #1 |
|--|------------------|----------|----------------|------------------------------|
| Informed Consent | R | | | |
| FSFI Survey | R | | | |
| Medical History | | S | | |
| Medication History | | S | R | |
| Pelvic Exam | | S | | |
| Focused Sexual Health Questions | | S | | |
| Sexual Health Plan of Care, Education, and Referrals | | S | | |
| FSFI Survey | | | | R |

5.2 Study Design and Duration

Patient Cohort

The study design is an evidence-based practice (EBP) study and includes the implementation and evaluation of a nurse led sexual health clinical program via the FSFI survey. The duration of study participation is 12 weeks. The goal for patients is to have 80% of participating patients to complete pre and post surveys and APP visit as part of their sexual health clinical program, with 30% of patients reporting improvement in sexual dysfunction via the FSFI score.

Nurse Cohort

The study design is an EBP study and includes two surveys in the Registered Nurse participants that includes KAP and EPBSE. The duration of study participation is 4 weeks. The goal is to have 100% of the gynecology oncology registered nurses to participate in the survey and sexual dysfunction education.

5.3 Description of Study Procedures

Patient Cohort

The study involves the participation of patients at multiple time points. The study procedures will assess the patients sexual function using the FSFI prior to the APP sexual health visit and post APP sexual health visit and telephone follow up call. Patients will be recruited through clinical chart identification.

This study involves the participation of registered nurses at multiple time points. The study procedures will assess the nurses' knowledge and confidence using the KAP and EPSE survey before sexual health program and again post education at the end of the study. The survey results will remain anonymous for both the pre and post-test. Nurse subjects will be recruited via email, and staff weekly huddles to complete both surveys.

Medical Record/Clinical Record Review:

Patient Cohort

This study involves review of medical records of patients included in this study. The questionnaire will be administered once at baseline (prior to the APP visit) and at the end of the study (after the telephone follow up call performed 8-10 weeks post APP visit). The study will collect sensitive information. This information is routinely collected per standard of care as as part of clinical care on a regular basis. A study code will be included on the questionnaire. The questionnaire will not be linked to each other and will be administered at two different time points.

- Female Sexual Function Index (FSFI)
 - o The FSFI is a validated tool that addresses five domains: desire, subjective arousal, lubrication, orgasm, satisfaction, and pain/discomfort. It encompasses nineteen self-measurement items that provides a score on overall levels of sexual function (Meston et al., 2020).
- Chart review to count the number of referrals and treatments for sexual dysfunction before and after the nurse led sexual health clinical program intervention

Nurse Cohort- N/A

Education:

Nurse Cohort

- The educational content will come from the After Cancer Solutions for Sexual Health Program, a non-profit developed with input from a cancer survivor and specialists to provide evidence-based education for providers and patients (After Cancer, 2025). The program, including the "About Us" pilot and "30 Second Message Workshop," is active across Iowa and aims to normalize sexual health discussions, build provider confidence, and guide appropriate referrals (After Cancer, 2025).
 - o 30 second message workshop
 - o Access to "About Us" sexual dysfunction patient and provider handouts
 - o National Comprehensive Cancer Network Sexual Health Guidelines

Questionnaires/Surveys:

Patient Cohort:

We will be doing the following questionnaires for patient participants:

- Female Sexual Function Index (FSFI)
 - o The FSFI is a validated tool that addresses five domains: desire, subjective arousal, lubrication, orgasm, satisfaction, and pain/discomfort. It encompasses nineteen self-measurement items that provides a score on overall levels of sexual function (Meston et al., 2020).

Nurse Cohort:

We will be doing the following questionnaires for nurse participants:

- Knowledge, Attitude, and Practice Survey in Healthcare (KAP), and the Evidence Based Nursing Practice Self-Efficacy Scale (EPSE).
 - o The questionnaire is not available in languages other than English.
 - The KAP survey is a validated tool that assess knowledge and attitudes about a specific health topic, to identify areas where education efforts need to be applied (Andrade et al., 2020).
 - The EBPSE survey is a validated tool which assesses and monitors nurses' confidence in their ability to implement evidence-based practice (EBP) skills (Tucker et al., 2009).

The study will be conducted at one site only, Cedars-Sinai.

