Information sheet will be given to nurses using REDcap. Nurses will be recruited to participate in the electronic pre and or post survey and informed they may self-select to participate in the project by clicking the survey link and QR code provided to them. A waiver of documentation of informed consent is being requested. By clicking the link, this implies their consent to participate. Nurses will be informed that they may withdraw from participating in the project at any time by exiting the survey. All nurses in the Gynecology Oncology Outpatient Cancer Clinic will receive Sexual Dysfunction training. However, only nurses who agree/consent to the pre-and post-education surveys (KAP & EBPSE) will be involved in the survey.

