6.4 Confidentiality and Security of Data

- **Secure Storage**: Data will be housed in a HIPAA-compliant secure storage system, like REDCap or Box, within the Cedars-Sinai network with access restricted to approved members of the research team.
- **Limited Access:** Private identifiable information will be accessible only to IRB approved study team members with current IRB training.
- Unique ID Numbers and Coding: Each patient will be assigned a unique ID number. The linking list will be kept secure. Direct identifiers listed in section 8 will be separated from the study materials (data and/or specimens) as soon as possible. During data abstraction, name and/or MRN are required for data verification purposes. After data abstraction is complete and data have been verified, the name will be removed (if collected). Only the MRN will be used to link the study ID/code to the individual after that point until the linking list is destroyed.
- **Destroying Identifiers:** The identifiers and the linking list will be destroyed as soon as scientifically possible and maintained only as long as necessary to abstract, analyze and verify data.

- **Storage of Physical Records:** Physical records will be maintained for this study at a secure location where access is limited to approved personnel. The records will not be removed from Cedars-Sinai premises.
- **Retention/Destruction of Study Materials:** Study data/materials will be kept and/or destroyed according to applicable policy.
- **Sharing Data:** One or more investigators with access to non-identifiable data are not at Cedars-Sinai. They will be an advisor to the project and assist with data analysis.

Patient Cohort

The data that will be shared with the collaborating institution/research will include patient information as follows: patient's age, gender, race, marital status, medical history, hospital Diagnosis, date of treatment, date of surgery, date of radiation, prior reports of sexual dysfunction, and prior referrals. The collaborating institution will assist with analyzing the data, writing up the project and results, and disseminating the results.

Nurse Cohort

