8.3 Statistical Analysis Methodologies

Patient Cohort

- This pilot study will obtain estimates of the following parameters:
- The patient subjects will be, at most, 35 subjects due to the available population and limited timeframe.

- In this survey/questionnaire study, we will assess patients' sexual function in aggregate form.
- The FSFI addresses five domains to include desire and subjective arousal, lubrication, orgasm, satisfaction, and pain/discomfort. It encompasses nineteen self-measurement items that provides a score on overall levels of sexual function (Meston et al., 2020). A Likert scale is used from 1 to 5, with higher scores indicating greater levels of sexual function on the specific item. FSFI is scored in two ways; individual domains and total FSFI score by taking a sum of all scores (Meston et al., 2020).
- We hypothesize that 30% of participants have an improvement in FSFI scores indicated by a ½ standard deviation.
- The project will utilize both QI Macros and Intellectus Statistics to measure the changes in patient sexual function. The analysis will incorporate statistical methods such as run charts, control charts, and t-tests to assess sexual function in patients before and after the intervention. More specifically regarding t-tests with the FSFI tool, we will compare pre and post intervention using paired t-tests.

- The nurse subjects will be at most five.
- In this survey/questionnaire study, we will assess nurses' responses in aggregate form. The KAP survey is comprised of 24 items, each assessed using a 4-point likert scale (Xie et al., 2023).
- Participants evaluate their knowledge and skills on a scale ranging from 1 (inadequate) to 4 (more than adequate). Similarly, they rate the frequency of their practice for each item, from 1 (never) to 4 (almost always). Scores for each subscale, knowledge, attitudes, and practices, range from 24 to 96 (Xie et al., 2023). The total score for the KAP survey is obtained by summing the scores across all subscales, with higher scores indicating greater levels of knowledge, more positive attitudes, and more consistent practices (Xie et al., 2023).
- We hypothesize that 50% of nurses have an increase in KAP scores indicated by a ½ standard deviation.

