- In the next survey, EBPSE, we will assess nurses' responses in aggregate form. The EBPSE survey is comprised of 17 items designed to help nurse process information and develop essential EBP skills. Each item is rated on how confident one can perform the activity with percentage numbers 0-100 likert scale (Tucker et al., 2009).
- We hypothesize that 50% of nurses have an increase in EBPSE scores indicated by a ½ standard deviation.
- The project will utilize both QI Macros and Intellectus Statistics to measure the changes in nurses' knowledge and self-efficacy. The analysis will incorporate statistical methods such as run charts, control charts, and t-tests to evaluate changes in participants' knowledge and self-efficacy. More specifically regarding t-tests, the EBPSE will use a paired sample t-test, and the KAP survey will use t-tests to compare pre and post survey responses.

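### Nurse surveys are anonymous with no linking key described, yet Section 8.3 plans a paired EBPSE t-test and per-nurse ½ SD shares for KAP and EBPSE

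*Protocol*

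**What the plan says.** - **Anonymity.** Section 5.3, on the nurse surveys: "The survey results will remain anonymous for both the pre and post-test".
- **Identifiers.** Section 6.4: "Each patient will be assigned a unique ID number". The linking list there runs through the medical record number, so it cannot serve nurses. The study code mentioned in Section 5.3 stands under the patient cohort, in a part marked not applicable to nurses. The nurse data elements in Section 6.3 are age, gender, work unit, position and time in position, with no ID or code. Section 4.3.1 brings nurses in through a survey link and QR code, again with no code mentioned.
- **Analysis.** Section 8.3: "the EBPSE will use a paired sample t-test, and the KAP survey will use t-tests to compare pre and post survey responses".
- **Hypotheses.** Section 8.3: "We hypothesize that 50% of nurses have an increase in KAP scores indicated by a ½ standard deviation" and "We hypothesize that 50% of nurses have an increase in EBPSE scores indicated by a ½ standard deviation".
- **Who completes what.** Section 4.3.1 first says "Nurses will be recruited to participate in the electronic pre and or post survey", then that "only nurses who agree/consent to the pre-and post-education surveys (KAP & EBPSE) will be involved in the survey". Section 5.3 agrees with the second statement: "Nurse subjects will be recruited via email, and staff weekly huddles to complete both surveys". Section 8.1 also aims for all nurses to complete both surveys.
- **Size.** Section 8.2 gives at most five nurses.

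**The concern.** A paired t-test works on each nurse's difference between post and pre. The share of nurses who improve by ½ SD is also counted nurse by nurse, even though it is reported as one aggregate figure. Two unlinked anonymous lists give the pre and post distributions but not the differences.

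The group means that bear on the secondary objective remain available. What is lost is the one test named as paired and both numerical hypotheses for the nurse outcomes. No other numerical target is set for those outcomes; the 100% goal in Sections 5.2 and 8.1 concerns participation.

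Timing makes this more than an analysis detail to be left to a later plan. The key has to be on the form when the first survey is answered. Afterwards the only route to matching is through personal characteristics, which undoes the anonymity promised to the nurses.

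The pre-and/or-post wording in Section 4.3.1 is a smaller conflict, but it points the same way: a nurse who answers only one survey cannot contribute a change.

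**Working it through.** The protocol gives no power, alpha, SD or calculated sample size for nurses, so it has no figure to reproduce. The check has three steps.

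**1. What each planned result needs**

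| Planned nurse result (Section 8.3) | Data needed | Available from unlinked forms? |
|---|---|---|
| EBPSE paired t-test | each nurse's difference | no |
| 50% gain ½ SD on EBPSE | each nurse's difference | no |
| 50% gain ½ SD on KAP | each nurse's difference | no |
| KAP t-test (type not stated) | differences if paired, two lists if unpaired | only if unpaired |
| Group means, pre and post | two lists | yes |

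**2. Can the two lists alone settle the answer?**

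The scores are assumed for illustration: EBPSE pre 40, 50, 60, 70, 80 and post 50, 60, 70, 80, 90. The protocol does not say which SD is meant, so I take the pre-score SD.

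- Pre mean 60; SD = √[(400 + 100 + 0 + 100 + 400)/4] = √250 = 15.81; ½ SD = 7.91.
- Mean gain = 70 − 60 = 10, whatever the matching.
- There are 5! = 120 ways to match the lists. The number of nurses gaining at least 7.91 points is:

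| Nurses improving | 1 of 5 | 2 of 5 | 3 of 5 | 4 of 5 | 5 of 5 |
|---|---|---|---|---|---|
| Matchings | 1 | 26 | 66 | 26 | 1 |

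- The 50% hypothesis fails in 1 + 26 = 27 matchings and is met in 66 + 26 + 1 = 93.
- Leaving out the one matching in which every change is equal (zero variance of change), the paired p-value runs from 0.034 to 0.519 over the other 119. It is below 0.05 in 4 of them.

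A second assumed set behaves the same way. With pre 50, 55, 60, 65, 70 and post 53, 60, 63, 70, 74 (½ SD = 3.95), the share improving runs from 20% to 80% and the paired p-value from 0.0009 to 0.61. The unpaired p-value is 0.46 throughout.

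**3. What linkage would buy**

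Paired power at n = 5 comes from the noncentral t with 4 degrees of freedom and noncentrality √5 × d/√[2(1 − r)], where d is the gain in SD units and r the pre-post correlation. Two-sided alpha 0.05, d and r are all assumed.

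| Gain d | r = 0 | r = 0.5 | r = 0.7 | r = 0.9 |
|---|---|---|---|---|
| 1 SD | 23% | 40% | 59% | 95% |
| ½ SD | 9% | 14% | 20% | 48% |

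An observed 3 of 5 improving has an exact (Clopper-Pearson) 95% CI of 15% to 95%. Linkage makes the planned results computable but does not make them precise.

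**The case against.** The strongest reply is that anonymous does not mean unlinked. A code known only to the nurse pairs the forms without identifying anyone, and Section 5.3 says outright that the patient questionnaires are not linked while saying no such thing for nurses. On that reading only a survey-build detail is missing. It is true that anonymity and pairing can coexist, and the fix relies on it. But no such code appears in any section where it would belong, and a team that follows the text would collect forms it cannot pair.

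Some narrower points stand:

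- The KAP t-test is not called paired, so an unpaired version could be run. The KAP conflict comes only from the ½ SD share.
- The scores are invented, and few matchings in the first set reach p < 0.05. The illustration shows that the results are undetermined, not that matching usually decides significance. Some data sets, such as every post score far above every pre score, would fix the share without a link, but a plan cannot count on that.
- Five nurses might be matched on age, gender and tenure if those are recorded with each survey. That is not planned. It would also weaken anonymity, since Section 6.4 shares these fields with the collaborating institution.
- The 50% figures are worded as hypotheses, and no decision rule hangs on them. With at most five nurses in a local practice project, the stakes are low.

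**Conclusion.** The concern holds. The EBPSE paired test and the two ½ SD shares cannot in general be obtained from the nurse data that the protocol describes; group means and an unpaired KAP comparison can. This follows from the text alone and rests on no assumed number. The size of the ambiguity (1 to 5 of 5 improving, 27 matchings against 93 on the 50% hypothesis) is illustrative and depends on the assumed scores and on taking ½ of the pre-score SD. The point should be fixed rather than treated as critical: it touches a secondary objective in at most five nurses, but the loss is hard to undo once unlinked surveys are in.

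**What to change.** Before the first nurse survey:

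- Add a self-generated code, known only to the nurse, to both REDCap surveys, and describe the nurse data as coded in Sections 5.3 and 6.4.
- In Section 8.3, specify the within-nurse analysis for both EBPSE and KAP. Report it in aggregate, as the mean change with a 95% CI and the share improving.
- Do not list individual nurses' changes, and do not match on age or tenure.
- In Section 4.3.1, change the pre-and/or-post wording to require both surveys, in line with the rest of the protocol.

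If unlinked anonymity must stay, or the pre survey has already gone out without a code, delete the paired test and both 50% hypotheses and report pre and post group means only.

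The cost is one field per survey and wording in Sections 4.3.1, 5.3, 6.4 and 8.3 and in the nurse information sheet. Anonymity is slightly reduced in a group of at most five whose age, gender and tenure are also collected, and a forgotten code loses that nurse's pair. The fallback costs only deletions.

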3.0 Study Purpose and Objectives

Patient Cohort

The primary objectives of this study are to implement and evaluate the effectiveness of a nurse led clinical program to improve sexual dysfunction among gynecological cancer survivors. The patient's outcomes will be measured via the Female Sexual Function Index (FSFI).

The secondary objectives of this study are to improve gynecologic cancer nurses' knowledge and confidence in the topic of sexual dysfunction screening, treatment, and referral using the Knowledge, Attitude, and Practice Survey in Healthcare (KAP), and the Evidence Based Nursing Practice Self-Efficacy Scale (EPSE).

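### Section 5.3 says the pre and post FSFI forms will not be linked, but Section 8.3 needs them matched within patient for the paired t-test and the ½ SD responder goal

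*Protocol*

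**What the plan says.** Section 3.0 makes the FSFI the measure of the primary patient objective. Section 5.3, under the patient cohort, has it completed before the APP visit and again at the end of the study. On data handling it says "A study code will be included on the questionnaire", and in the next sentence "The questionnaire will not be linked to each other and will be administered at two different time points".

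Section 8.3 says of the same instrument that "we will compare pre and post intervention using paired t-tests", and sets the target: "We hypothesize that 30% of participants have an improvement in FSFI scores indicated by a ½ standard deviation". The 30% improvement goal also appears in Sections 5.2 and 8.1.

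Section 4.3.1 limits the study to women who have both surveys and the APP visit. Section 6.4 says "Each patient will be assigned a unique ID number" and describes a linking list tied to the medical record number. It does not say that the ID or the list will be used to join the two FSFI forms.

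**The concern.** A paired t-test works on each woman's own difference, post minus pre. A share of women who improved by ½ SD needs a change score classified woman by woman. If the two forms are not linked, neither quantity exists. Only the two separate score distributions do.

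FSFI change is the only patient outcome named in Section 3.0, so the conflict reaches the main patient result. If the surveys are built to the letter of Section 5.3, the only t-test left treats the same women as two independent groups, and the responder goal cannot be assessed. If the team links the forms anyway, it departs from a written statement about how sensitive data are handled.

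**Working it through.** **What each planned element needs**

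| Element | Where | Within-patient match needed? |
|---|---|---|
| Paired t-test, FSFI pre vs post | Section 8.3 | Yes |
| 30% improving by ½ SD | Sections 5.2, 8.1, 8.3 | Yes |
| Analysis set with both surveys and the visit | Section 4.3.1 | Yes, to identify its members |
| Data rule for the two FSFI forms | Section 5.3 | States there is no link |

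No later text withdraws the Section 5.3 rule. Section 8.3 also says sexual function is assessed in aggregate. That is compatible with a paired analysis reported in aggregate, but it does not supply the missing pairs.

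**Size of the effect.** The protocol gives no alpha, power, SD or correlation, so there is no figure of its own to reproduce. The inputs are:

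- From Section 8.1: 35 recruited and 80% completing, so 35 × 0.80 = 28 pairs. The goal of 30% is 0.30 × 28 = 8.4 women.
- Assumed: bivariate normal scores, equal SD at both times, two-sided alpha 0.05, a true mean gain of 0.5 SD for the power figures, pre-post correlation r varied, and ½ SD taken as half the SD of the FSFI score.

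**Standard error of the mean change, in SD units**

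- Paired: √(2(1 − r)/28), which is 0.267 at r = 0, 0.189 at r = 0.5 and 0.085 at r = 0.9.
- Unpaired: √(2/28) = 0.267 whatever r is.
- Ratio: 1/√(1 − r), which is 1.41 at r = 0.5 and 2.24 at r = 0.8.

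**Power and type I error** (simulation, 28 pairs, 40,000 replicates; the unpaired test is applied to the same correlated data)

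| r | Paired power | Unpaired power | Unpaired type I error |
|---|---|---|---|
| 0.5 | 0.72 | 0.43 | 0.0071 |
| 0.6 | 0.81 | 0.43 | 0.0028 |
| 0.7 | 0.91 | 0.42 | 0.0008 |
| 0.8 | 0.98 | 0.41 | 0.0001 |

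At lower correlation the gap narrows: 0.58 against 0.44 at r = 0.3, and 0.52 against 0.45 at r = 0.2. At r = 0 pairing gains nothing.

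**Responder share.** P(change ≥ 0.5 SD) = 1 − Φ((0.5 − m)/√(2(1 − r))), where m is the mean gain in SD units.

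| m | r = 0 | r = 0.5 | r = 0.7 | r = 0.9 |
|---|---|---|---|---|
| 0 | 36% | 31% | 26% | 13% |
| 0.25 | 43% | 40% | 37% | 29% |

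Within a row the pre and post distributions are identical and only r differs. Unlinked forms carry no information on r, so the same two distributions can lie above or below the 30% goal. The responder share is therefore not identified.

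**The case against.** The best case for the plan is that, read as a whole, it points to matched data. The questionnaire carries a study code, each patient has a unique ID, the linking list is kept for as long as analysis needs it, the analysis set requires both surveys, and paired t-tests are named. The patient forms are coded, whereas the nurse surveys are expressly anonymous. The disputed sentence is ungrammatical and might mean only that the FSFI is given on two separate occasions.

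This shows that matching is feasible and probably intended. It does not remove the conflict. The denial of a link comes directly after the mention of the code, its literal reading is the natural one, and no text says the same code is on both forms. On the linking list, Section 6.4 says "Only the MRN will be used to link the study ID/code to the individual after that point until the linking list is destroyed". That ties a code to a person, not one form to the other, and once the list is gone late repair may not be possible.

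Four further points stand as limits:

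- Section 8.3 does not label these analyses primary; that status follows from Section 3.0.
- Counts of referrals and treatments, listed among the primary procedures in Section 1.0, do not depend on linking the forms.
- The protocol plans no unpaired FSFI test and makes no power claim for this pilot, so the power figures only illustrate what is left if the rule is followed.
- For positive r the unpaired test is conservative, so the harm is lost sensitivity and not false positives.

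**Conclusion.** The concern holds. Sections 5.3 and 8.3 contradict each other on the main patient outcome, and as written neither the paired t-test nor the ½ SD responder share can be computed. That conclusion needs no numerical assumption.

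The loss from falling back on an unpaired test does rest on assumptions. With 28 completers, a 0.5 SD gain and r from 0.5 to 0.8, power falls from 72–98% to about 41–43%, and actual type I error is 0.7% or less against a nominal 5%. Below r = 0.5 the loss is smaller. The defect is a correctable contradiction and not an established loss of data, but it must be settled because forms collected without a common code may not be pairable afterwards.

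**What to change.** In Section 5.3, replace the sentence that denies the link with: *The same patient study code will appear on the pre and post FSFI forms and will be used to link them within patient; the paired t-test and the ½ SD responder classification use the linked pairs.* Keep the list that ties codes to medical record numbers separate, as Section 6.4 already provides.

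Before making the change, check whether the consent text tells patients their forms will not be linked; if it does, it must be changed too. If the forms must stay unlinked for confidentiality, Section 8.3 has to change instead: drop the paired t-test and the responder goal, and state the limits of an unpaired comparison.

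The cost of the preferred change is one sentence and possibly a minor IRB wording amendment. The study code and REDCap are already in the plan.
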